### 7.4 HANDLING OF MISSING DATA

#### 7.4.1 Safety

With respect to safety evaluations, it is not planned to impute missing values.

#### 7.4.2 Plasma/urine drug concentration - time profiles

Handling of missing PK data will be performed according to the relevant Corporate Procedure of the Sponsor ([001-MCS-36-472](#)).

Drug concentration data identified with NOS (no sample available), NOR (no valid result), NOA (not analysed), or BLQ (below the lower limit of quantification will be displayed as such and not replaced by zero at any time point (this rule also applies also to the lag phase, including the predose values).

### **7.4.3 Pharmacokinetic parameters**

Handling of missing PK data will be performed according to the relevant SOP of the Sponsor ([001-MCS-36-472](#)).

Drug concentration data identified with NOS, NOR or NOA will generally not be considered. Concentration values in the lag phase identified as BLQ will be set to zero. All other BLQ values of the profile will be ignored. The lag phase is defined as the period between time zero and the first time point with a concentration above the quantification limit.

### **7.5 RANDOMISATION**

Randomisation is not applicable in this open-label single arm study. All subjects will receive the same treatment. A list of consecutive subject numbers for SD and MD subjects separately will be provided (see [Section 4.1.2](#) for details of allocation of subject numbers to subjects).

### **7.6 DETERMINATION OF SAMPLE SIZE**

For this exploratory study, no prospective calculations of statistical precision or power have been made. The planned sample size of 8 subjects per treatment group has been selected for practical reasons and is judged as being adequate to get reliable results regarding the trial objectives.

## **8. INFORMED CONSENT, DATA PROTECTION, TRIAL RECORDS**

The trial will be carried out in compliance with the protocol, the principles laid down in the Declaration of Helsinki, in accordance with the ICH Harmonised Tripartite Guideline for Good Clinical Practice (GCP) and relevant BI SOPs.

The investigator should inform the sponsor immediately of any urgent safety measures taken to protect the study subjects against any immediate hazard, and also of any serious breaches of the protocol or of ICH GCP.

The rights of the investigator and of the sponsor with regard to publication of the results of this trial are described in a separate agreement between the investigator or the trial site and the sponsor. As a general rule, no trial results should be published prior to finalisation of the CTR.

Insurance Coverage: The terms and conditions of the insurance coverage must be given to each subject and are made available to the investigator via documentation in the ISF.

### **8.1 STUDY APPROVAL, SUBJECT INFORMATION, AND INFORMED CONSENT**

This trial will be initiated only after all required legal documentation has been reviewed and approved by the respective Institutional Review Board (IRB) / Independent Ethics Committee (IEC) and competent authority (CA) according to national and international regulations. The same applies for the implementation of changes introduced by amendments.

Prior to a subject's participation in the trial, written informed consent must be obtained from each subject (or the subject's legally accepted representative) according to ICH GCP and to the regulatory and legal requirements of the participating country. Each signature must be personally dated by each signatory and the informed consent and any additional subject information form are to be retained by the investigator as part of the trial records. A copy of the signed and dated written informed consent and any additional subject information must be given to each subject or the subject's legally accepted representative.

The subject must be informed that his personal trial-related data will be used by Boehringer Ingelheim in accordance with the local data protection law. The level of disclosure must also be explained to the subject.

The subject must be informed that his medical record may be examined by authorised monitors (Clinical Monitor Local/Clinical Research Associate) or Clinical Quality Assurance auditors appointed by Boehringer Ingelheim, by appropriate IRB/IEC members, and by inspectors from regulatory authorities.

### **8.2 DATA QUALITY ASSURANCE**

A quality assurance audit/inspection of this trial may be conducted by the sponsor or sponsor's designees, by IRBs/IECs, or by regulatory authorities. The quality assurance

auditor will have access to all medical records, the investigator's trial-related files and correspondence, and the informed consent documentation of this clinical trial.

The data management procedures to ensure the quality of the data are described in detail in the trial data management and analysis plan (TDMAP) available in the TMF.

### **8.3 RECORDS**

CRFs for individual subjects will be provided by the sponsor. For drug accountability, refer to [Section 4.1.8](#).

#### **8.3.1 Source documents**

Source documents provide evidence for the existence of the subject and substantiate the integrity of the data collected. Source documents are filed at the investigator's site.

All data reported in the CRFs must be consistent with the source data or the discrepancies must be explained.

The investigator may need to request previous medical records or transfer records, depending on the trial.

#### **8.3.2 Direct access to source data and documents**

The investigator/institution will permit trial-related monitoring, audits, IRB/IEC review and regulatory inspection, providing direct access to all related source data/documents. CRFs and all source documents, including progress notes (if applicable) and copies of laboratory and medical test results must be available at all times for review by the sponsor's clinical trial monitor, auditor and inspection by health authorities (e.g. FDA). The Clinical Research Associate/on site monitor and auditor may review all CRFs, and written informed consents. The accuracy of the data will be verified by reviewing the documents described in [Section 8.3.1](#).

#### **8.3.3 Storage period of records**

Trial site:

The trial site must retain the source and essential documents (including ISF) according to the national or local requirements (whatever is longer) valid at the time of the end of the trial.

Sponsor:

The sponsor must retain the essential documents according to the sponsor's SOPs.

### **8.4 EXPEDITED REPORTING OF ADVERSE EVENTS**

BI is responsible to fulfil their legal and regulatory reporting obligation in accordance with regulatory requirements.

## **8.5 STATEMENT OF CONFIDENTIALITY**

Individual subject medical information obtained as a result of this trial is considered confidential and disclosure to third parties is prohibited with the exceptions noted below. Subject confidentiality will be ensured by using subject identification code numbers.

Treatment data may be provided to the subject's personal physician or to other appropriate medical personnel responsible for the subject's welfare. Data generated as a result of the trial need to be available for inspection on request by the participating physicians, the sponsor's representatives, by the IRB/IEC and the regulatory authorities, i.e. the CA.

## **8.6 COMPLETION OF TRIAL**

The EC / competent authority in each participating EU member state needs to be notified about the end of the trial (last subject / subject out, unless specified differently in [Section 6.2.3](#) of the CTP) or early termination of the trial.

## 10. APPENDICES

### 10.1 RADIATION BURDEN CALCULATION

Radiation Burden Calculation Report

BI1467335

### Calculation of Radiation Burden (Dosimetry)

### Appendix A1: Radiation burden of the gastrointestinal tract after oral administration of 2.0 MBq C BI1467335

Using SEE-values, an organ-specific radiation burden can be estimated. The SEE-value is dependent, among other factors, on the mass of the target organ and the type of radiation.

With these SEE-values and the number of disintegrations U in the target organ, the organ dose equivalent Hi is calculated:

Hi = constant x U x SEE (mSv); using a target organ-related weight factor, the contribution of the organ burden to the body burden is translated as: Hwb,t = Hi x weight factor (mSv)

In order to be able to calculate the radiation burden of the GI tract, this has been divided in five sections, i.e., the stomach (st), the small intestines (si), the right part of the large intestines, the left part of the large intestines (lc) and the rectum / sigmoid (rs).

The SEE-values for these organs are:

ST:	1.0 x 10  ,	(weight factor = 0.12)
SI:	3.2 x 10  ,	(weight factor = 0.01)
RC:	2.3 x 10  ,	(weight factor = 0.048)
LC:	2.9 x 10  ,	(weight factor = 0.045)
RS:	9.2 x 10  ,	(weight factor = 0.027)

The number of disintegrations U in each target organ depends on the amount of radioactivity excreted, or any metabolites that are eliminated via the gall bladder that is standardised for the various compartments of the GI tract (constant). I0 = 2.0 MBq; Excretion via GI tract: 23% of the dose, excretion via urine: 77% of the dose. These assumptions give:

H st =	0.0016 mSv
H si =	0.0000 mSv
H RC =	0.0000 mSv
H Lc =	0.0000 mSv
H RS =	0.0000 mSv
total GI:	0.0016 mSv

The total contribution of the GI tract to the effective dose (body radiation burden) amounts to 0.0016 mSv.

### Appendix A2: Radiation burden of the central compartment after oral administration of 2.0 MBq C BI1467335

Average body weight = 70 kg; SEE = 7.1905 x 10^-7; 100% of the orally administered dose is absorbed and 85.9% (100% minus the percentages of the separately calculated organs/tissues) of the dose is excreted with a half-life of 80 hours. Total number of disintegrations in the central compartment after oral administration of 2.0 MBq [C]BI1467335 is 707 x 10^9 with a tissue weighting factor of 0.77 giving a Htw of 0.0610 mSv.

Radiation Burden Calculation Report

BI1467335

### Appendix A3: Radiation burden of the liver and kidneys after oral administration of 2.0 MBq C BI1467335

For the liver SEE =  $2.72 \times 10^{-5}$ ; 8.5% of the dose administered orally, excreted with a half-life of 73 h, with a tissue weighting factor of 0.05 giving a Htw of 0.0139 mSv.

For the kidney SEE =  $1.58 \times 10^{-4}$ ; 2.2% of the dose administered orally, excreted with a half-life of 100 h, with a tissue weighting factor of 0.05 giving a Htw of 0.0286 mSv.

For the uveal tract SEE =  $8.84 \times 10^{-2}$ ; 0.22% of the dose administered orally, excreted with a half-life of 140 h, with a tissue weighting factor of 0.01 giving a Htw of 0.45 mSv.

For the stomach SEE =  $1.0 \times 10^{-5}$ ; 3.2% of the dose administered orally, excreted with a half-life of 150 h, with a tissue weighting factor of 0.12 giving a Htw of 0.01 mSv.

The contribution to the radiation burden of these four organs/tissues is  $0.0139 + 0.0286 + 0.45 + 0.01 = 0.5025$  mSv

The total effective dose (radiation burden) of a single oral dose of C-labeled BI1467335 containing 2.0 MBq C-activity, based on the above-mentioned worst case scenario amounts to 0.56 mSv.

Name and Date:

Signature:

09 November 2017

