### 3. DESCRIPTION OF DESIGN AND TRIAL POPULATION

#### 3.1 OVERALL TRIAL DESIGN AND PLAN

The study will be performed as an open-label, single-arm and single- or multiple dose trial in healthy male subjects in order to investigate the basic pharmacokinetics of BI 1467335, and [C]-radioactivity, including mass balance following a single oral dose of [C]BI 1467335. For subjects assigned to the multiple dose treatment, the single oral dose of [C]BI 1467335 is dosed following multiple dosing of cold drug (Days 1-27 and 29-last dose given based on radioactive recovery, maximum Day 40).

The planned radioactive dose per subject is 2.0 MBq (54 µCi).

For the single dose part Day 1 is the day of [C] labelled drug administration. Subjects will stay in the study centre up to the morning of day 15 for the collection of samples of blood, urine, and faeces. Subjects will be readmitted to the study centre for 24 h collection intervals of urine and faeces on days 21, 28, 35, 42, and 49, if release criteria have not been met. Within 24 h before each of these once-weekly in-house collection intervals, subjects are to collect faeces at home. This 24 h interval home collection faeces will be used for analysis in case no defecation occurs in the subsequent 24 h in-house collection interval.

For the multiple dose part Day 28 is the day of [C] labelled drug administration. Non-labelled compound will be administered at site or at home during Day 1 to Day 27 and from Day 29 to Day 40 (dosing may be stopped before Day 40 if release criteria based on [C]-radioactivity have been reached for individual subjects, see below). From the evening of Day 27 to the morning of Day 43 subjects will remain in the study centre for the entire duration. Subjects will be released from the centre on Day 43. Subjects will then be readmitted to the study centre for 24 h collection intervals of urine and faeces on days 49, 56, 63, 70, and 77, if release criteria have not been met. Within 24 h before each of these once-weekly in-house collection intervals, subjects are to collect faeces at home. This 24 h interval home collection faeces will be used for analysis in case no defecation occurs in the subsequent 24 h in-house collection interval.

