#### 4.1.3 Selection of doses in the trial

A dose of 10 mg, administered either as single or multiple dose, is considered adequate for the objectives of the current trial.

The dose on Day 1 (SD) or Day 28 (MD) administered as oral solution will include 2.0 MBq (54 µCi) of [C]-radiolabelled BI 1467335. The radiolabeled dose of 2.0 MBq is required to provide sufficient analytical sensitivity to enable metabolite quantification in a sufficiently low range. The total effective dose (radiation burden) amounts to 0.56 mSv. This is below the limit of 1.0 mSv and considered acceptable. Radiation burden calculations are presented in [Appendix 10.1](#). For risk-benefit assessment, see [Section 2.3](#).

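### Appendix 10.1 gives label retained in stomach tissue an SEE that implies a 5 kg stomach, so the stomach term and the 0.56 mSv total are understated.

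*Protocol*

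**What the plan says.** Appendix 10.1 builds the effective dose from three parts.

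- **A1** covers the gastrointestinal tract. It explains that "The SEE-value is dependent, among other factors, on the mass of the target organ and the type of radiation", lists the stomach SEE with its weight as "1.0 x 10 -5 , (weight factor = 0.12", and arrives at 0.0016 mSv.
- **A2** covers the central compartment ("Average body weight = 70 kg", SEE 7.1905 x 10^-7). It takes the oral dose as fully absorbed and assigns 85.9% of it here, after subtracting the organs calculated separately. The result is 0.0610 mSv.
- **A3** covers liver, kidney, uveal tract and stomach. The stomach entry uses an SEE of 1.0 x 10^-5 for "3.2% of the dose administered orally, excreted with a half-life of 150 h, with a tissue weighting factor of 0.12". Its printed result is 0.01 mSv, and the four terms add to 0.5025 mSv.

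The appendix gives the total as 0.56 mSv and calls it a worst case. Section 2.3 compares this figure with an acceptable level of 1.0 mSv or less for healthy volunteers. Section 4.1.3 uses it to support the 2.0 MBq dose: "This is below the limit of 1.0 mSv and considered acceptable".

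**The concern.** The stomach has the longest half-life of any compartment in the appendix, a larger retained fraction than the kidneys or uveal tract, and the largest weighting factor of the four A3 organs. Yet its contribution is the smallest of the four. The cause is the SEE, which is lower than the liver's even though the stomach is the smaller organ. It equals the A1 entry, where the source is activity in transit.

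The 0.56 mSv figure is what the protocol offers to justify exposing healthy men, who receive no therapeutic benefit, to 2.0 MBq. If one organ term is too low, the total is not a worst case and the stated margin of 1.0 - 0.56 = 0.44 mSv is too generous.

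**Working it through.** **1. Reproduce the printed terms.** Activity is 2.0 MBq (Section 3.1); fractions f, half-lives T, SEEs and weights w are from A3. A1 writes the organ dose as a constant times U times SEE. I take the constant as 1.602 x 10^-10 Sv per MeV/g and

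U = 2.0 x 10^6 x f x T x 3600 / ln 2, H_w = 1.602 x 10^-10 x U x SEE x w.

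For the stomach, U = 2.0 x 10^6 x 0.032 x 150 x 3600 / 0.6931 = 4.986 x 10^10. Then H_w = 1.602 x 10^-10 x 4.986 x 10^10 x 1.0 x 10^-5 x 0.12 = 9.6 x 10^-6 Sv = 0.0096 mSv.

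| Organ | f | T (h) | SEE | w | Recomputed (mSv) | Printed (mSv) |
|---|---|---|---|---|---|---|
| Liver | 8.5% | 73 | 2.72 x 10^-5 | 0.05 | 0.0140 | 0.0139 |
| Kidney | 2.2% | 100 | 1.58 x 10^-4 | 0.05 | 0.0289 | 0.0286 |
| Uveal tract | 0.22% | 140 | 8.84 x 10^-2 | 0.01 | 0.453 | 0.45 |
| Stomach | 3.2% | 150 | 1.0 x 10^-5 | 0.12 | 0.0096 | 0.01 |

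So 1.0 x 10^-5 really was used; it is not a misprint. The printed parts sum to 0.0016 + 0.0610 + 0.5025 = 0.5651 mSv, against 0.56 stated. Separately, the A2 term of 0.0610 matches the stated 707 x 10^9 disintegrations with weight 0.75; the stated 0.77 gives 0.0627. That difference of about 0.002 mSv is left aside, and the printed 0.0610 is used below.

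**2. Implied organ masses.** With one nuclide, SEE x mass should be constant for label held in tissue. A2 supplies the constant: 7.1905 x 10^-7 x 70,000 g = 0.0503 MeV. Dividing by each SEE:

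- liver: 0.0503 / 2.72 x 10^-5 = 1850 g
- kidneys: 0.0503 / 1.58 x 10^-4 = 319 g
- uveal tract: 0.0503 / 8.84 x 10^-2 = 0.57 g
- stomach: 0.0503 / 1.0 x 10^-5 = 5033 g

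Three organs fit one basis. The stomach is 5033 / 1850 = 2.7 times the liver.

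**3. Is the 3.2% in tissue or in gut contents?**

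- A2 starts from 100% absorption and removes the separately calculated organs: 100 - 8.5 - 2.2 - 0.22 - 3.2 = 85.88%, the stated 85.9%. The stomach's 3.2% is therefore part of the absorbed dose.
- A3 groups the stomach with the other three organs and gives it a 150 h half-life.
- Passage through the gut is already counted in A1. Its 0.0016 mSv corresponds to about 1.2 h of the full 2.0 MBq in the stomach.

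**4. Recalculate with a tissue SEE.** Put SEE = 0.0503 / m for stomach mass m. The term becomes 0.00958 x 5033 / m = 48.2 / m mSv (m in grams). The other printed terms sum to 0.0016 + 0.0610 + 0.0139 + 0.0286 + 0.45 = 0.5551 mSv. The masses are assumptions.

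| Assumed mass (g) | Stomach term (mSv) | Total (mSv) | Margin to 1.0 (mSv) |
|---|---|---|---|
| 1850 (implied liver mass) | 0.026 | 0.58 | 0.42 |
| 500 | 0.10 | 0.65 | 0.35 |
| 250 | 0.19 | 0.75 | 0.25 |
| 150 | 0.32 | 0.88 | 0.12 |
| 120 | 0.40 | 0.96 | 0.04 |
| 100 | 0.48 | 1.04 | -0.04 |

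The total reaches 1.0 mSv at m = 48.24 / (1 - 0.5551) = about 108 g.

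**The case against.** Every printed organ product reproduces to rounding, so this is a challenge to an input, not to the multiplication. A1 says SEE depends on more than mass. Inverting its other gut values gives absurd masses: 0.0503 / 3.2 x 10^-7 is 157 kg for the small intestine, and 0.0503 / 2.3 x 10^-10 is about 219 tonnes for the right colon. Those SEEs plainly describe a different source geometry, so the 5 kg figure is not a claim anyone made, and everything depends on where the 3.2% sits. The origin of the 3.2% and 150 h is not shown, and the available text of the dosimetry report may be incomplete ahead of A1. Finally, no stomach mass is given, and across 120 to 250 g the total stays below 1.0 mSv, so the decision to give 2.0 MBq would stand.

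The point about geometry is right, but it supports the concern: a gut-transit SEE should not be applied to absorbed label. On location, A2's subtraction and A3's grouping settle the matter within the report's own structure, and nothing visible points the other way. What stands is that the size is conditional on an assumed mass, that the masses tabulated are illustrative, and that a breach of the limit is not shown.

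**Conclusion.** The concern holds. A3 applies a gut-transit SEE to label that the report itself treats as absorbed and retained in tissue. The direction follows from the documents alone: the stomach term and the total are understated for any stomach lighter than 5 kg.

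The size needs a mass the documents do not give. For 120 to 250 g the total is 0.96 to 0.75 mSv, and the margin falls from 0.44 to between 0.04 and 0.25 mSv. At 150 g the stomach becomes the second-largest contributor after the uveal tract, about 34 times its printed value on unrounded figures (0.3216 / 0.0096). These results assume that energy divided by organ mass is the right basis for the stomach, as it is for the other three organs, and they keep the other printed terms unchanged. The figure should be corrected because the benefit-risk statement relies on it.

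**What to change.** Ask the dosimetry provider to recalculate the A3 stomach term with an SEE for activity in stomach tissue, on the basis used for liver, kidney and uveal tract, and to state the organ mass. If the provider believes 1.0 x 10^-5 is correct for this source, the report should say why. Then restate the total in Appendix 10.1, Section 2.3 and Section 4.1.3 and repeat the comparison with 1.0 mSv.

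The cost is one recalculation and three text edits. The stated radiation burden will look less favourable. If the provider's mass were below about 108 g, the 2.0 MBq dose itself would need to be reconsidered.

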## 11. DESCRIPTION OF GLOBAL AMENDMENT(S)

Number of global amendment		1
Date of CTP revision		26 February 2018
EudraCT number		2017-002879-26
BI Trial number		1386-0011
BI Investigational Product(s)		BI 1467335
Title of protocol		A phase I, open-label, single and multiple dose trial to investigate metabolism and pharmacokinetics of [  C]BI 1467335 administered as oral solution in healthy male volunteers
To be implemented only after approval of the IRB / IEC / Competent Authorities		
To be implemented immediately in order to eliminate hazard – IRB / IEC / Competent Authority to be notified of change with request for approval		
Can be implemented without IRB / IEC / Competent Authority approval as changes involve logistical or administrative aspects only		
Section to be changed		
 
1. Synopsis
 
2. Section 4.2.2 Restrictions
 
3. Section 5.2.2 Methods of sample collection
 

Description of change		
 
1. Inconsistency in description of PK sampling. During multiple dose, samples for C radioactivity not before Day 28, instead of “at all time points”.
 
2. Restriction of poppy seeds.
 
3. During multiple dose, samples for C radioactivity not before Day 28 and sampling procedures accordingly modified.
 

Number of global amendment		1
Rationale for change		Minor inconsistencies in the methods of PK sampling required a protocol revision. To avoid false positive drug screens during the treatment period, the restrictions were amended to include a restriction on poppy-seed containing products. In the context of this amendment, a few further inconsistencies have been corrected.

Number of global amendment		2
Date of CTP revision		14 March 2018
EudraCT number		2017-002879-26
BI Trial number		1386-0011
BI Investigational Product(s)		BI 1467335
Title of protocol		A phase I, open-label, single and multiple dose trial to investigate metabolism and pharmacokinetics of [  C]BI 1467335 administered as oral solution in healthy male volunteers
To be implemented only after approval of the IRB / IEC / Competent Authorities		
To be implemented immediately in order to eliminate hazard – IRB / IEC / Competent Authority to be notified of change with request for approval		
Can be implemented without IRB / IEC / Competent Authority approval as changes involve logistical or administrative aspects only		
Section to be changed		Flow Chart 1.2 Drug profile 4.2.2 Restrictions
Description of change		Flow Chart: Elimination of inconsistencies Section 1.2: Implementation of new in vitro data classifying BI 1467335  Section 4.2.2: Addition of prohibited foods to mitigate the risk of relevant adverse reactions.
Rationale for change		

Number of global amendment		2
		
In the context with this amendment we have also included missing ticks in the flow chart as already described in the foot note # 10.

**APPROVAL / SIGNATURE PAGE****Document Number:** c17932132**Technical Version Number:**3.0**Document Name:** clinical-trial-protocol-revision-02

**Title:** A phase I, open-label, single and multiple dose trial to investigate metabolism and pharmacokinetics of [14C]BI 1467335 administered as oral solution in healthy male volunteers

